3. CHARACTERISTICS OF THE RESEARCH POPULATION

3.1. Subject Characteristics

- (a) **Number of Subjects:** The study subjects include nephrologists, research coordinators, patient coaches, patients, and caregivers from Strong, Highland, FF Thompson, and Rochester General Hospital. The study will be performed between August 2021 and September 2025. Nephrologists (n= up to 16), in the Strong, Highland, FF Thompson, and Rochester General Renal Group will be eligible to participate and will provide informed consent. For physicians who withdraw from the study prior to the enrollment of their own participating patients, they will be replaced with additional physicians, therefore keeping the number of participating physicians up to 16. Research Coordinators (n=up to 3) who have assisted in the study will be eligible to participate in a qualitative interview and will provide informed consent. Patient Coaches (n=up to 3) who have assisted in the study will be eligible to participate in a qualitative interview and will provide informed consent. With a total sample size of 60 patients (approximately 5 patients per nephrologist depending on the total number of enrolled nephrologists), we would have 80% power at an alpha of 0.05, assuming a coefficient of variation of cluster sizes as high as 0.5 and an intraclass correlation coefficient of 0.1 to detect mean differences of at least 15 points (standard deviation 11) on the OPTION scale scores reflecting shared decision making between two groups. The data generated in this pilot study will be useful to generate effect size estimates for a future trial. We expect to enroll 36 caregivers assuming a 60% participation rate of caregivers. The proposed recruitment plan aligns with the goals of the K-23 which is a small pilot.

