11. DATA ANALYSIS AND MONITORING

11.1. Planned Statistical Analysis

This is a pilot cluster-randomized trial, where our communication outcomes (APPC scores) ³²

and shared decision-making outcomes (OPTION scores)⁴⁰ are measured at the level of the physician-patient dyad, while other outcomes (e.g., SDM questionnaire)⁴¹ are measured at the level of the patient for descriptive analyses but adjusted for the clustering effect in final analyses. All analyses will be performed using SAS (version 9.4, Cary, NC). Patient and physician characteristics will be described using proportions for categorical variables and means (\pm standard deviations) or medians (interquartile range) for continuous variables. **Quantitative analyses (Aims 1-2):** Analyses of the Feasibility and Acceptability of the Intervention Measures (**Aim 1**) will be mainly descriptive. To compare group differences for the study outcomes (**Aim 2**), we will use Wald-type tests from pre-specified mixed-effects linear regression models for continuous outcomes and generalized linear models with logit link function for binary outcomes. *Analyses will be specified to account for the nesting of patients (the units of analysis) within physicians (the units of randomization).* For all regression analyses, physician-level covariates for gender, years of experience, practice style, prior communication skills training, and the renal fellow status will be included, as well as patient-level covariates to adjust for demographic characteristics. All reported p values will be two sided, with $p < 0.05$ considered statistically significant. **Qualitative analyses (Aim 1):** Using Atlas.ti software, interviews of patients (30 minutes) and nephrologists (15 minutes) will be transcribed, de-identified, and verified for accuracy by a third party. Based on a modified phenomenological approach,¹⁵² I will work with [name], MPH (data manager), under [name] supervision, will create a coding scheme to characterize barriers, strengths, and areas of improvement for the proposed intervention and study design. Ten initial transcripts will be read and reread to reach an agreement. Disagreements will be resolved by discussion with the mentoring team. Remaining transcripts will be coded according to the coding scheme. **Handling of missing data:** The regression approach requires the "missing completely at random" (MCAR) assumption for valid inference, which may not be met for some outcomes in this study. Therefore, we will apply the response-dependent missingness—or the missing at random (MAR)—assumption when outcomes and missing data are less likely to be independent. We will examine the nature of the missing data and use the inverse probability weighting (IPW) approach, or multiple imputation, and sensitivity analyses, if necessary.

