	Decisional engagement scale	Hoerger et al, Psychol Assess. 2016	10	0-3 months 3-6 months at Study completion

	Choice of renal replacement therapy modality	NA	1	Study entry 0-3 months 3-6 months at Study completion
	Prognostic discussion	Weeks et al, JAMA 1998	10	Study entry 0-3 months 3-6 months at Study completion
	Decisional Conflict scale	Med Decis Making. 1995	10	Study entry 0-3 months 3-6 months at Study completion
	Goal Concordant Care Questionnaire	Curtis et al	2	Study entry 0-3 months 3-6 months at Study completion
Other potential co-variates	Demographics	NA	17	Study entry
	Cavanaugh dialysis knowledge scale – Rochester version	Cavanaugh et al, CJASN 2009	14	Study entry 0-3 months 3-6 months at Study completion
	Human connection scale	Mack et al Cancer 2009	16	Study entry 0-3 months
	Healthcare climate questionnaire	XX	5	Study entry 0-3 months
	Quality of life (KDQOL)		32	Study entry 0-3 months 3-6 months at Study completion
	Control preference scale- Rochester version	Degner et al, Can J Nurs Res. 1990	1	Study entry
	Health literacy	Davis et al, family medicine, 1991	6	Study entry
	Trust - Primary Care Assessment Survey (PCAS) trust subscale	Safran DG, Kosinski M, Tarlov AR, Med Care. 1998;	8	Study entry 0-3 months 3-6 months at Study completion
	KARNOFSKY SELF-REPORTED PERFORMANCE	Crooks at al. J Gerontol. 1991;	1	Study entry 3-6 months at Study completion
	OARS Comorbidity	Fillenbaum et al. J Gerontol. 1981;	15	Study entry
	Press Ganey Patient Satisfaction Questionnaire	NA	16	Study entry 0-3 months
	Perceived Efficacy in Patient-Physician Interactions	JAGS, April 2015	5	Study entry 0-3 months 3-6 months at Study completion

	Advanced care planning	NA	4	Study entry 3-6 months at Study completion
--	------------------------	----	---	--

	Hospitalizations	NA	2	Study entry 0-3 months 3-6 months at Study completion
	Exit interview	NA	3	Upon withdrawal

Table 7. Assessments and timing of administration of assessments for caregivers

	Assessment	References if applicable	# of items	Time of completion
Aim-1	Feasibility (patients approached vs enrolled)	Weiner et al, Implement Science, 2017	Feasibility of the intervention measure	0-3 months (after last coaching session)
			Feasibility of the Question Prompt List	
			Feasibility of the Education Booklet	
			Feasibility of Education video	
	Acceptability	NA	Qualitative interviews	0-3 months (after last coaching session)

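### Section 11.1 leaves out the study-entry value of the patient outcomes that have one, and wrongly says that the regression approach needs MCAR

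*Combined protocol and SAP*

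**What the plan says.** Section 11.1 (Planned Statistical Analysis) compares arms with mixed-effects linear models for continuous outcomes and logit models for binary ones, with patients nested in physicians. For every regression it names five physician covariates (gender, experience, practice style, prior communication training, fellow status), "as well as patient-level covariates to adjust for demographic characteristics". It names no entry value of the outcome and no within-patient covariance, and it does not say which follow-up time is analysed.

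Table 6 gives the timing "Study entry 0-3 months 3-6 months at Study completion" for four Aim 2 patient measures: treatment choice, prognostic discussion, Decisional Conflict and goal-concordant care. The Shared Decision-Making Questionnaire and the Decisional Engagement Scale are taken at the two follow-up times only. OPTION and APPC are listed once, at completion, from visit audio.

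On missing data, Section 11.1 calls MCAR a requirement of the regression approach, an "assumption for valid inference, which may not be met for some outcomes in this study". It then moves to MAR and names inverse probability weighting or multiple imputation, plus sensitivity analyses, to be used where needed once the missing data have been examined.

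**The concern.** A patient's Decisional Conflict at entry is probably the best single predictor of the same score later. Demographics will rarely replace it. The unit of randomisation is the nephrologist: up to 16 in Section 3.1, about 12 in Section 9.1. With so few clusters, the arms can easily differ at entry, and an unadjusted model passes part of that difference into the effect estimate. The pilot exists partly to supply effect sizes for a larger trial (Sections 2.2 and 3.1), so noise here carries forward.

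The MCAR sentence matters for a related reason. If the team believes its main model fails without MCAR, it will look for a remedy after seeing the data. A likelihood-based mixed model on all follow-up visits is already valid under MAR, so it can be fixed in advance. Outcome-related missingness is plausible, because Section 7 allows withdrawal of patients whose kidney disease worsens acutely.

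**Working it through.** **Inputs from the documents.** "With a total sample size of 60 patients", "approximately 5 patients per nephrologist depending on the total number of enrolled nephrologists", hence about 12 nephrologists; ICC 0.1; a "coefficient of variation of cluster sizes as high as 0.5"; SD 11 and a 15-point OPTION difference (all Section 3.1); two-sided 5% tests (Section 11.1).

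**Assumptions not in the documents.** 1:1 allocation (30 patients per arm), no dropout, an entry/follow-up correlation r of 0.3 to 0.7 that is the same at cluster and patient level, and the OPTION ICC applied to the other outcomes.

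**The plan's own figure.** Design effect = 1 + ((1 + 0.5²) × 5 − 1) × 0.1 = 1.525. Effective n per arm = 30/1.525 = 19.7. SE = 11 × √(2/19.7) = 3.51 points, and 15/3.51 = 4.28. Power is about 99.0% (normal) or 97.0% (t, 10 df), against the statement that "we would have 80% power at an alpha of 0.05". The stated 80% is not reproduced and looks conservative. Nothing below depends on it, because OPTION has no entry score.

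**Chance imbalance at entry.** The SE of the arm difference in entry means is √(2 × 1.525/30) = 0.32 SD. The chance of an imbalance above 0.3 SD is P(|Z| > 0.3/0.319), about 35%. Without adjustment, about r times the imbalance enters the estimate: 0.5 × 0.3 = 0.15 SD at r = 0.5.

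**Gain from entry adjustment.** The variance factor is 1 − r², the interval-width factor is √(1 − r²), and the equivalent N is 60/(1 − r²). The detectable difference at 80% power (normal) is 2.80 × 0.319 × √(1 − r²).

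| r | Variance factor | Width factor | Equivalent N | Detectable difference, normal (SD) | Same, t with 10 df (SD) |
|---|---|---|---|---|---|
| none | 1.00 | 1.00 | 60 | 0.89 | 0.99 |
| 0.3 | 0.91 | 0.954 | 66 | 0.85 | 0.95 |
| 0.5 | 0.75 | 0.866 | 80 | 0.77 | 0.86 |
| 0.7 | 0.51 | 0.714 | 118 | 0.64 | 0.71 |

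**Missing data.** A simulated stress case used 12 nephrologists with 5 patients each, three visits and a true effect of 0.50 SD. At the last visit 39% of scores were missing, depending on the 0-3 month score in opposite directions by arm. Variance components were treated as known. Mean estimates (Monte Carlo SE at most 0.009):

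- last visit, complete cases: 0.10
- the same plus entry score: 0.29
- both follow-up visits, no entry score: 0.50
- all three visits, entry means constrained equal: 0.50

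The mechanism is MAR and not MCAR, and the likelihood models that include the 0-3 month score recover the true effect. It is that score which removes the bias; the entry score alone does not. The missingness pattern was chosen to be severe and is not a forecast.

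**The case against.** **The plan does not rely on MCAR.** A reader might infer from the MCAR sentence that it does. The documents do not support that: Section 11.1 says MCAR may fail, moves to MAR and names two suitable methods. The sentence also covers the logit models, where it may be fairer if they are fitted as unweighted marginal models. And if only one follow-up score is modelled, a patient who lacks it contributes no outcome. What remains is a sentence that is wrong for the linear mixed model, and a choice of method left until the data have been seen.

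**Entry scores are not true baselines.** Patients join after their nephrologist is randomised and, in the intervention arm, after at least two coaching sessions (Section 5.1). They must already have seen that nephrologist (Table 4), who may decline their participation (Section 4.1). Prognostic discussion and goal-concordant care at entry could therefore reflect contact with a trained nephrologist, and adjustment would remove about r times any effect already present. This stands. It rules out a model constraining entry means to be equal as the primary analysis, and it calls for an unadjusted result alongside for those two outcomes. It is weaker for Decisional Conflict.

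**The gain is assumed and partial.** The values of r are not in the documents, and the table compares with no adjustment, whereas the plan already adjusts for demographics and physician factors. The real increment could be smaller. This also stands. So does the context: the primary aim is feasibility, acceptability and fidelity.

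**Conclusion.** The point holds for a limited set of outcomes. Section 11.1 omits an entry value that is already collected for patient Decisional Conflict, prognostic discussion and goal-concordant care, and its MCAR statement is wrong for the likelihood-based linear mixed model. For continuous outcomes, variance would fall by about 9%, 25% or 49% at assumed correlations of 0.3, 0.5 and 0.7, before allowing for what the planned covariates already explain. Using the entry value is a cheap improvement and should be made.

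A reader might infer three things that the documents do not support:

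- **That all of Aim 2 is affected.** Four of its eight patient measures have no entry score: OPTION, APPC, the Shared Decision-Making Questionnaire and the Decisional Engagement Scale.
- **That one longitudinal model settles everything.** OPTION and APPC are listed at one time only. Treatment choice has three categories. Goal-concordant care has two items and no stated scoring, and 1 − r² does not carry over to binary or categorical outcomes.
- **That the same criticism covers caregivers.** Section 11.1 confines its group comparisons to Aim 2 and gives no analysis specific to Aim 3. Table 7 lists caregiver Decisional Conflict among potential covariates. That is a separate gap.

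**What to change.** Amend Section 11.1 as follows.

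1. **Continuous patient outcomes with an entry value, Decisional Conflict first.** The primary analysis is one REML mixed model on both follow-up visits, with time, arm-by-time, entry score as a covariate, the planned covariates, a random nephrologist intercept, a within-patient covariance and small-sample degrees of freedom. State that it is valid under MAR given the data it includes. Multiple imputation or weighting become sensitivity analyses.
2. **Entry means.** Do not make a model that constrains them to be equal the primary analysis.
3. **Prognostic discussion and goal-concordant care.** State the scoring, and also report the result without entry adjustment.
4. **Treatment choice and any binary-scored outcome.** Use a categorical or logit mixed model with the entry value.
5. **Shared Decision-Making Questionnaire and Decisional Engagement Scale.** Use the two-visit model without an entry term; the benefit is for missing data only.
6. **OPTION and APPC.** Pre-specify imputation or weighting, naming the method and the auxiliary variables. This change brings them nothing else.
7. **MCAR sentence.** Replace it with a statement of the assumption behind each model.

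The cost is SAP wording, with no new data. The protocol should state that the entry survey is completed before coaching and before the recorded visit. The remaining downside is that adjustment may remove a small part of any effect already present at entry.

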1. PURPOSE OF THE STUDY AND BACKGROUND

1.1. Objective:

The objectives of this study proposal are:

Aim 1 (primary): Assess the feasibility, acceptability, and fidelity of the DIAL-SDM intervention, as measured in both nephrologist and patient coaching sessions by the Feasibility of the Intervention Measure,¹ Acceptability of the Intervention Measures,¹ and fidelity checklists for both nephrologist and patients' coaching sessions. We will also gather qualitative data from nephrologists, patient coaches, research coordinators, patients, and caregivers to guide the modification of the study protocol.

Aim 2: Generate preliminary effect sizes and examine the effect of the intervention on the following patient outcomes:

- (a) **Active patient participation in dialysis decision-making**, as measured by the Active Patient Participation Coding (APPC) scores from audio recordings of office visits.^{2,3}
- (b) **Shared dialysis decision-making**, as measured by the modified OPTION scale scores,⁴ from audio recordings of office visits, and the patient-reported Shared Decision-Making Questionnaire and the Decisional Engagement Scale.⁵
- (c) **Patients' initial choice of ESRD treatment options** (home vs. in-center dialysis vs. CM) at study entry and completion.
- (d) Patient report of **prognostic discussions**, as measured by the prognosis questionnaire.⁶
- (e) **Decisional conflict**, as measured by the decisional conflict scale.⁷
- (f) **Patient report of goal concordant care**, as measured by the goal concordant questionnaire.⁸

Aim 3: Aim 2: Generate preliminary effect sizes and examine the effect of the intervention on the following caregiver outcomes:

- (a) **Decisional conflict**, as measured by the decisional conflict scale.⁶
- (b) **Shared dialysis decision-making** as measured by the Shared Decision-Making Questionnaire and the Decisional Engagement Scale.^{4,5}

1.2. Background:

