
Table 5. Timing of administration of assessments for physicians

	Measurement	References (if applicable)	# of items	Time of completion
Aim-1	Feasibility, acceptability and appropriateness of the intervention measures	Weiner et al, Implement Science, 2017	12	Study completion
	Fidelity of the DIAL-SDM intervention	NA	30	After the completion of each coaching session.
	Qualitative Interviews		7	Study completion
Aim-2	Physician-patient communication: Active Patient Participation Coding (APPC) scores	Street et al, Soc Sci Med. 2007	NA	Study completion (audio scripts)
	Shared decision-making: OPTION scale	Elwyn G, Qual Saf Health Care. 2003	12	Study completion (audio scripts)
	Comfort with shared decision making	Degner et al, J of Clin Epidemiology, 1992	5	Study entry Study completion
	Comfort with medical paternalism	Duberstein et al, JOSM 2019	1	Study entry
Other potential co-variates	Physician demographics and training experience	NA	7	Study entry
	Value Affirmation Exercise		9	Study entry (Intervention group)

Table 6. Timing of administration of assessments for patients

	Assessment	References if applicable	# items	Time of completion
Aim-1	Feasibility (patients approached vs enrolled)	Weiner et al, Implement Science, 2017	Feasibility of the intervention measure	0-3 months (after last coaching session)
			Feasibility of the Question Prompt List	
			Feasibility of the Education Booklet	
			Feasibility of Education video	
	Acceptability	NA	Qualitative interviews	0-3 months (after last coaching session)
		Weiner et al, Implement Science, 2017	Acceptability of the Intervention measure	0-3 months (after last coaching session)
			Acceptability of the Question Prompt List	
			Acceptability of the Education Booklet	
		NA	Fidelity	After the coaching session (audio recordings)
Aim-2	Physician-patient communication: Active Patient Participation Coding (APPC) scores	Street et al, Soc Sci Med. 2007	NA	3-6 months at Study completion (audio scripts)
	Shared decision-making: OPTION scale	Elwyn G, Qual Saf Health Care. 2003	12	3-6 months at Study completion (audio scripts)
	Shared decision-making questionnaire	Kristen L et al. Patient Educ Couns. 2010	9	0-3 months 3-6 months at Study completion

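### Section 11.1 calls every Aim 2 result with p<0.05 significant, across eight patient outcomes, most at two follow-ups, with no lead outcome, lead time point, adjustment or exploratory label

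*Combined protocol and SAP*

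**What the plan says.** Section 1.1 makes Aim 1 (feasibility, acceptability and fidelity) the primary aim. Aim 2 is to "Generate preliminary effect sizes and examine the effect of the intervention on the following patient outcomes". The list under it contains eight measures: APPC, OPTION, the Shared Decision-Making Questionnaire, the Decisional Engagement Scale, treatment choice, prognostic discussion, decisional conflict and goal-concordant care.

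For the Aim 2 group comparisons, section 11.1 says "we will use Wald-type tests from pre-specified mixed-effects linear regression models for continuous outcomes", with logit-link models for binary outcomes. It closes with one rule for everything: "All reported p values will be two sided, with $p < 0.05$ considered statistically significant".

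Table 6 sets the timing:
- APPC and OPTION appear once, at "3-6 months at Study completion (audio scripts").
- The Shared Decision-Making Questionnaire and the Decisional Engagement Scale appear at "0-3 months 3-6 months at Study completion".
- Treatment choice, prognostic discussion, decisional conflict and goal-concordant care appear at "Study entry 0-3 months 3-6 months at Study completion".

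Aim 2(c) describes treatment choice differently: "home vs. in-center dialysis vs. CM) at study entry and completion", which is one follow-up rather than two.

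Section 3.1(a) sizes the trial on one outcome, with 80% power "to detect mean differences of at least 15 points (standard deviation 11) on the OPTION scale scores". Section 11.1 does not carry that precedence into the analysis.

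**The concern.** The significance rule has no exception, and nothing in the plan ranks the comparisons it covers. Any one of the Aim 2 outcomes, at either follow-up where there are two, could be reported as a statistically significant effect. The chance that at least one crosses p<0.05 is then well above 5% even if the intervention does nothing. The descriptive primary aim does not act as a gate for these tests.

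There is a second consequence. Section 3.1(a) says the pilot data will supply effect size estimates for a later trial. If the outcome or time point carried forward is chosen because it looked best, its estimate will be too large on average.

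**Working it through.** **Inputs from the document.** Two-sided 0.05 for each test (section 11.1). Eight Aim 2 patient outcomes (section 1.1). Two outcomes with one follow-up and six with two (Table 6), which gives 2 + 6×2 = 14 arm comparisons. If Aim 2(c) governs treatment choice, the count is 3 + 5×2 = 13. For the design: 60 patients, about 5 per nephrologist, ICC 0.1, coefficient of variation of cluster size 0.5, SD 11 and difference 15 on OPTION (section 3.1(a)).

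**Assumptions.** The correlation between test statistics (the document gives none), 1:1 allocation, every null hypothesis true, and each single test holding exactly its 5% level. Caregiver outcomes (Aim 3) are not counted.

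**The plan's own figure.** The plan states no family-wise error rate. Its only design figure is the 80% power for OPTION:
- Design effect = 1 + ((1 + 0.5²)×5 − 1)×0.1 = 1.525.
- Effective n per arm = 30/1.525 = 19.7.
- SE = 11×√(2/19.7) = 3.5 points, and 15/3.5 = 4.28.
- Power is about 99% by the normal approximation, or 97% by a t test on 10 degrees of freedom.

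The 80% does not reproduce, but it errs on the cautious side and does not enter the error rates below.

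**Family-wise error, independent tests.** 1 − 0.95^k:
- k = 8: 33.7%
- k = 13: 48.7%
- k = 14: 51.2%

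**Family-wise error, equal correlation ρ.** 1 − ∫ φ(u) [Φ((1.96 − √ρ·u)/√(1−ρ)) − Φ((−1.96 − √ρ·u)/√(1−ρ))]^k du:

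| Tests | ρ = 0 | ρ = 0.5 | ρ = 0.8 |
|---|---|---|---|
| 8 (one per outcome) | 33.7% | 25.0% | 15.7% |
| 13 | 48.7% | 33.4% | 19.2% |
| 14 | 51.2% | 34.8% | 19.7% |

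**A more realistic structure.** Take correlation 0.5 between outcomes and 0.7 between the two follow-ups of one outcome. By simulation, 14 tests give about 33.6% and 13 give about 32.4%. If the correlation between different outcomes also weakens across time (0.5×0.7), the figures are about 36% and 34%.

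**Direction.** All these rates count a significant result in either direction. The chance of at least one false result in favour of the intervention is about half: 16-18% in the structured cases.

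**Two time points on one outcome.** k = 2 gives 9.1% at ρ = 0.5 (9.8% at 0, 7.8% at 0.8).

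**Effect size, only if the best is picked afterwards.** The SE of a standardised difference is √(4×1.525/60) = 0.319. The expected maximum of eight independent standard normals is 1.42. At ρ = 0.5 it is 1.42×√0.5 = 1.007. The best-looking of eight null outcomes would therefore be expected to show 1.007×0.319 = 0.32 SD in the favourable direction.

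**The case against.** The strongest reply is that this is a pilot. Aim 1 is primary and mainly descriptive, Aim 2 is there to produce preliminary effect sizes, and section 2.2 ties the larger trial to feasibility and acceptability. No decision rule says that one significant Aim 2 result means success. This stands. A reader might infer from the error rates that the trial has a one-in-three chance of a false positive conclusion. The documents do not support that, because no trial-level conclusion rests on an Aim 2 p value.

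The count of 13 or 14 tests is also an inference. Section 11.1 does not say whether the two follow-ups are tested separately or modelled jointly. This stands too, so the one-test-per-outcome figures come first. A single flat figure such as 34% would be misleading: it arises both from eight independent tests and, nearly, from fourteen correlated ones, and both rest on assumed correlations.

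The upward bias is conditional. No passage says that the best result will be selected, and Aim 2 asks for estimates on every listed outcome. The point is only that nothing in the plan prevents such selection.

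Finally, OPTION could be called the implied lead outcome, since the trial is sized on it. Section 11.1 gives it no precedence, though, and its significance rule covers the other seven equally. The pilot setting limits the harm but does not make the rule in section 11.1 consistent with the purpose of estimation.

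**Conclusion.** The gap in the text is certain: one unqualified significance rule, eight patient outcomes, five or six of them at two follow-ups, and no lead outcome, lead time point, adjustment or exploratory label. Its size depends on assumptions. With one test per outcome, the chance of at least one false significant result is about 25% at correlation 0.5, within 16% to 34%. With separate tests at each follow-up it is about 32-35% at 0.5, within about 19% to 51%. Across these cases the rate is roughly three to ten times the nominal 5%.

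The consequence is a risk of over-reading an Aim 2 finding, and of planning the next trial on an inflated effect if the outcome or time point is selected after results are seen. The plan should be changed, but this is not a fatal flaw.

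**What to change.** Before outcome data are examined by arm, replace the blanket sentence in section 11.1 with wording that does the following:

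1. Names OPTION, the outcome the trial is sized on, as the single Aim 2 comparison tested at two-sided 0.05. Section 5.1 allows up to two recorded nephrology visits per patient, so the text must also say which visit's score is used when there are two.
2. Reports all other Aim 2 outcomes and time points as exploratory effect estimates with 95% confidence intervals and no claim of statistical significance.
3. Names one time point for each repeated instrument as the source of the effect size carried forward.
4. Reconciles Aim 2(c) with Table 6 on when treatment choice is assessed.

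Timing matters. Section 3.1(a) dates the study from August 2021 to September 2025, and section 5.2 refers to participants who have already completed it. If outcome data have already been seen, naming a lead outcome is no longer credible, and all Aim 2 p values should be labelled exploratory instead.

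The change is wording only and needs no new patients or data. OPTION keeps the full 0.05, so its power is unaffected. The cost is that the other Aim 2 results can no longer be called statistically significant, which fits a pilot meant to estimate effect sizes.
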